### **3.4 Study Design**

This is a multicentre longitudinal study. Exploratory outcomes will be address through mixed methods, including longitudinal, semi-structured interviews and observational structured surveys.

### **3.5 Study Statistics**

This study is planned as a descriptive study in an effort to quantify the psychological impact on ICU survivors of COVID-19. It is anticipated that the study will report its findings using descriptive methods in the absence of a comparator group.

Trajectories of anxiety, depression, and trauma symptoms will be estimated using growth curve analysis. To improve power, we will use the full range of anxiety, depression and trauma symptom scores (not cut-off scores). Growth modelling is latent variable covariance modelling to estimate the intercept (value of the initial observation) and slope (the rate of change from this observation over time) of a time series of mean scores. We will estimate full sample single class models (eg, assuming homogeneity across the sample) for each outcome. Initial fixed parameters will be; error variance constrained to equality across observations, mean intercept and slope constrained to zero, intercept and slope constrained to equality, and intercept and slope covariance constrained to zero. Parameters will be systematically relaxed in that order until good fitting models ( $CFI > .95$ ,  $RMSEA < .05$ ) are identified with maximum fixed parameters. Linear and quadratic slope models will be tested; linear models being defined as slope parameters 0, 1, 4, and 12 and quadratic slopes as 0, 1, 8 and 24.

We will estimate and predict individual survivors' slope and intercept scores. Scores will be calculated using the regression method, setting intercepts for observed variables to 0 and imposing equality of variance. We will then regress predictor variables onto intercept and slope scores for all outcomes to identify variables likely to determine trajectories of anxiety, depression and trauma symptoms.

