We anticipate that there will be a significant burden to healthcare systems as a result of psychological distress. Current national guidelines state that at-risk ICU survivors who have had an admission of more than 4 days should be invited to a follow up clinic 2-3 months after discharge from ICU (20). However, hospital and community based services to support ICU survivors in their recovery were limited before COVID-19, with some hospitals not even offering an ICU follow up clinic (21). The number of patients expected to require admission to ICU during COVID-19 is far beyond existing UK critical care capacity, and in the context of enhanced baseline societal anxiety, the potential volume of patients with post-ICU psychological distress could far exceed existing healthcare capacity overwhelming current services. In order to be able to expand services as necessary and support ICU survivors properly to help them regain their quality of life, and return to working and contributing to society, we must first identify how many, and to what extent patients are affected.

In this study, we aim to: 1. identify the proportion of COVID-19-positive critical care survivors who experience anxiety, depression and/or trauma symptoms up to 12 months after discharge from ICU, using validated tools; 2. identify predictors of post-ICU anxiety, depression and/or trauma in COVID-19 ICU survivors; 3. explore the experiences of critical care survivors following COVID-19 infection during their recovery phase, including perceptions about the care received and support available to them and 4. assess geographical differences in the availability and structure of follow-up services offered to critical COVID-19 survivors. This information may be used to inform healthcare systems about the psychological support required for survivors of this pandemic, and may inform healthcare planning for future pandemics.

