##### **Exploratory objectives:**

1. Identify demographic, clinical, physical and/or psychosocial predictors of depression, anxiety and/or trauma symptoms at 3-, 6- and 12-months after ICU discharge in patients being treated for COVID-19 within the ICU.
2. Assess the feasibility of using a self-reported questionnaire to assess anxiety, depression and/or trauma symptoms in patients following ICU admission with COVID-19.
3. Explore the experiences of critical care survivors following COVID-19 infection during their recovery phase, including perceptions about the care received and support available to them, using semi-structured interviews.
4. Assess geographical differences in the availability and structure of follow-up services offered to patients with critical COVID-19 after hospital discharge.
5. Gain feedback from the study team members on their involvement in this trainee-led study.

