### **3.6 Sample size**

There is no formal sample size required. Overall we aim to recruit until September 2022 or when 1000 patients have answered the questionnaire at all three time points, whichever occurs first. We will initially approach 20 intensive care units for participation. If necessary we will extend the number of recruiting units to facilitate reaching this recruitment target. We have factored in a 40% return rate, so we will have to send out 2500 questionnaires in order to achieve our target.

With the semi-structured interviews, based on previous experience of qualitative evaluation of psychological effects on patients, we anticipate theoretical saturation with about 40 participants.

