## **4. Recruitment and Withdrawal of Participants**

### **4.1 Recruitment**

Recruitment will take place at hospitals across the UK, and be conducted by junior doctors who are either training, or have a specialist interest, in intensive care medicine; and/or allied health professionals working in intensive care (including Advanced Critical Care Practitioners). Therefore, recruitment will be balanced within the demands of the clinical workload. It is intended that all patients discharged from a recruiting ICU, that were admitted and treated for COVID-19, will be given an information sheet explaining the study to them and explaining the possibility of receiving three questionnaires during the year following discharge. Where this is not feasible, every reasonable effort will be made to contact these patients prior to hospital discharge. All ICUs with members in the Trainee Research in Intensive Care (TRIC) will be invited to participate.

For the semi-structured interviews, identification of participants will be performed by the central research team by accessing the PIM-COVID REDCap database. Where patients have agreed to be contacted by phone or email, these contact details will be available within the REDCap database. Patients who have provided consent to be contacted will be approached by telephone or email to discuss their potential participation in the study. A written information sheet will be sent via email or post as per participants' preferences. Participants have been asked whether or not they are happy to be contacted as part of the 3, 6 and 12 month questionnaires; participants who have indicated they would not like to be contacted will not be approached.

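### Patients are recruited through ICUs but section 3.5 makes no provision for within-ICU correlation, so any intervals for the primary proportions may be too narrow

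*Combined protocol and SAP*

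**What the plan says.** Section 3.4 sets the design: "This is a multicentre longitudinal study". On the number of sites, section 3.6 says "We will initially approach 20 intensive care units for participation" and then "If necessary we will extend the number of recruiting units to facilitate reaching this recruitment target". Section 4.1 widens the invitation: "All ICUs with members in the Trainee Research in Intensive Care (TRIC) will be invited to participate". The number of units at the end is therefore open. The recruitment target, also in section 3.6, is: "Overall we aim to recruit until September 2022 or when 1000 patients have answered the questionnaire at all three time points, whichever occurs first". The same section states that no formal sample size is needed.

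Section 3.5 gives three pieces of quantitative analysis. Findings are to be reported descriptively, with no interval method named for the primary proportions. Symptom scores go into latent growth models: "We will estimate full sample single class models (eg, assuming homogeneity across the sample) for each outcome". Predictors are then regressed on each patient's estimated intercept and slope. None of the three mentions ICU or site as a fixed or random effect, a cluster-robust error, an ICC or a design effect, and no other section does so.

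**The concern.** Patients discharged from the same unit may resemble one another in ways that patients from different units do not. The protocol gives grounds to think this possible. The Introduction says that support after ICU was limited before the pandemic, "with some hospitals not even offering an ICU follow up clinic", and an exploratory objective is to "Assess geographical differences in the availability and structure of follow-up services offered to patients with critical COVID-19 after hospital discharge". Recruitment is done by local staff around their clinical work (section 4.1), and local teams may take questionnaire answers by telephone (section 5.2), so who responds, and how, can also differ by site. Delirium counts as present only if it was recorded in the notes (section 5.3), which depends on local charting.

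If the section 3.5 models are run as described with default model-based errors, patients are treated as independent. With positive within-ICU correlation, those errors are too small for the proportions, which are the primary outcome, and for any predictor that differs mainly between units. Readers planning services would then see more certainty than the data hold.

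**Working it through.** **The plan's own figure.** Section 3.6 expects a 40% return: 1000 / 0.40 = 2500 questionnaires, which reproduces. The document states no precision, power or design-effect figure, so there is nothing further to reproduce.

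**Inputs.** n = 1000 (section 3.6). p = 0.34, the Introduction's background figure for anxiety and for PTSD at 12 to 14 months after ICU admission, used here as an illustration because the plan makes no design assumption. Number of units k = 20 (the initial approach in section 3.6) and k = 60 (assumed, to represent extension). ICC assumed between 0 and 0.05. Equal unit sizes, m = n / k.

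**Formulas.**
- Design effect: DEFF = 1 + (m − 1) × ICC
- 95% half-width: 1.96 × √(DEFF × p(1 − p) / n)
- Actual coverage of an interval that ignores site: 2Φ(1.96 / √DEFF) − 1

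With site ignored, the half-width is 1.96 × √(0.34 × 0.66 / 1000) = 2.94 points.

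**20 units, m = 50.** For example, at ICC 0.01, DEFF = 1 + 49 × 0.01 = 1.49.

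| ICC | DEFF | Effective n | Half-width needed (points) | Coverage if site ignored |
|---|---|---|---|---|
| 0 | 1.00 | 1000 | 2.94 | 95.0% |
| 0.005 | 1.245 | 803 | 3.28 | 92.1% |
| 0.01 | 1.49 | 671 | 3.58 | 89.2% |
| 0.02 | 1.98 | 505 | 4.13 | 83.6% |
| 0.05 | 3.45 | 290 | 5.45 | 70.9% |

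**60 units, m = 16.7.**

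| ICC | DEFF | Effective n | Half-width needed (points) | Coverage if site ignored |
|---|---|---|---|---|
| 0.01 | 1.157 | 865 | 3.16 | 93.2% |
| 0.02 | 1.313 | 761 | 3.36 | 91.3% |
| 0.05 | 1.783 | 561 | 3.92 | 85.8% |

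If the September 2022 date stops recruitment early, units are smaller and the effect shrinks. With an assumed 400 patients in 20 units, m = 20 and DEFF at ICC 0.01, 0.02 and 0.05 is 1.19, 1.38 and 1.95, giving coverage of 93%, 90% and 84%.

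**Predictors.** For a predictor with its own between-unit correlation ICC_x, the variance inflation is approximately 1 + (m − 1) × ICC_x × ICC_y. With m = 50 and ICC_x = 0.1, ICC_y of 0.01, 0.02 and 0.05 gives 1.049, 1.098 and 1.245, so the standard error is understated by a factor of 1.02, 1.05 and 1.12. A simulation of ordinary least squares (20 units of 50, 4000 runs per setting, nominal 5% test) gave these type I error rates:

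| ICC of outcome | Purely patient-level predictor | Purely unit-level predictor |
|---|---|---|
| 0.01 | 5.4% | 11.0% |
| 0.02 | 5.1% | 16.1% |
| 0.05 | 5.4% | 29.4% |

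**The case against.** The case for leaving the plan alone has real substance.

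- **The homogeneity wording is not an independence assumption.** A reader might infer from the section 3.5 sentence that patients are declared independent across ICUs. It does not say that. It specifies one latent trajectory class, as opposed to a mixture of classes. The concern rests on the plan's silence about site.
- **No interval is planned for the proportions.** It would be wrong to say that the plan's intervals are too narrow, since it names none. This stands, and it makes the point conditional. A prevalence reported as the primary result will still need an interval, and its method is unspecified.
- **The ICC is unknown.** Differences in follow-up services do not show that HADS or IES-6 scores cluster by unit, and the geographical objective is met by a separate survey of UK units (section 5.2). A reader might conclude that intervals will be too narrow; the documents support only that they may be.
- **Twenty units is a starting figure.** The 20-unit results sit near the unfavourable end. Extra sites reduce the problem but, at the assumed ICCs, do not remove it.
- **Most listed predictors are patient-level.** Age, gender, comorbidities, APACHE II, CAS-1R and EQ-5D-5L are measured on the individual, and deprivation is looked up from each patient's postcode (section 7.1). A claim that predictor effects in general are compromised is not supported. These analyses are also labelled exploratory in section 3.2.
- **The remedy has limits.** Cluster-robust errors with 20 units and more than a dozen candidate predictors are unstable, because the rank of the estimated covariance is limited by the number of units.

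**Conclusion.** The point holds in a conditional form. Section 3.5 leaves within-ICU correlation unaddressed in the proportions, the growth models and the predictor regressions. If site is ignored and the ICC is between 0.01 and 0.05, a nominal 95% interval for a proportion near 34% from 1000 patients would cover about 89% to 71% with 20 ICUs, or 93% to 86% with 60. At an ICC of zero it would be correct. These figures rest on an assumed ICC, an assumed number of units, equal unit sizes and a background prevalence.

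For predictors, the effect is material only for variables that vary strongly between sites. Recorded delirium and benzodiazepine use are possible examples, but how far they vary by unit is itself an assumption. A reader might also infer that the recruitment target is invalidated. It is not, because no power or precision calculation was made for it.

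**What to change.** Amend section 3.5 as follows:

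1. Report each primary proportion with a 95% interval that uses ICU-clustered variance and a t multiplier on the number of units minus 1.
2. In the growth models and predictor regressions, include an ICU random intercept. Cluster-robust errors with a small-cluster correction are an alternative if the number of units is adequate for the number of predictors.
3. Report the ICC for each outcome. This also serves the feasibility outcome in section 3.3 on estimating quantities for future sample size calculations.

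The change is to wording and analysis code only. Local investigators already enter data hospital by hospital (section 7.2), so no new data should be needed and the sample size does not change. The cost is somewhat wider intervals, even if there is no clustering: with 20 units the t(19) multiplier is 2.093 against 1.96, and 2.093 / 1.96 = 1.07, about 7% wider. At an ICC of zero the half-width goes from 2.94 to about 2.94 × 1.068 = 3.14 points. With more units the penalty is smaller.

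### The growth-model relaxation order in section 3.5 can keep a false zero intercept-slope covariance and so distort slope variance; how much depends on a covariance the documents do not give

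*Combined protocol and SAP*

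**What the plan says.** Section 3.5 (Study Statistics) fits single-class latent growth models to the anxiety, depression and trauma scores. It lists the starting constraints in this sequence: "Initial fixed parameters will be; error variance constrained to equality across observations, mean intercept and slope constrained to zero", then "intercept and slope constrained to equality, and intercept and slope covariance constrained to zero". The rule for moving on is "Parameters will be systematically relaxed in that order until good fitting models" (CFI above .95 and RMSEA below .05) "are identified with maximum fixed parameters". So the first model to pass is kept, and the covariance is estimated only if every earlier model has failed.

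The slope codes are given as "linear models being defined as slope parameters 0, 1, 4, and 12", which is four codes; section 5.3 schedules questionnaires at three times (3, 6 and 12 months). Individual intercept and slope scores are then computed, "imposing equality of variance", and become the outcomes in the predictor regressions. Identifying predictors is a secondary objective in section 1 and an exploratory one in section 3.2. The primary objective is a proportion at 6 months.

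**The concern.** Two of the constraints have very different standing. Equal error variance across waves is a plausible simplification for one questionnaire given repeatedly. A zero covariance between starting level and rate of change is a substantive claim, and the documents offer no support for it. The order discards the first untested and protects the second.

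This follows from the constraint "mean intercept and slope constrained to zero". A HADS subscale cannot be negative (section 3.3), so its mean is zero only if everyone scores zero. Every model that keeps this constraint fails, and the error variances have already been freed by the time the means are. The first model with a real chance of passing under the planned order therefore has free error variances and still has "intercept and slope covariance constrained to zero".

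If that model passes when the covariance is not zero, the slope variance is misestimated. The slope scores are what the predictors are meant to explain, so the predictor analysis would work on a distorted outcome.

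**Working it through.** **Inputs from the documents.** The constraint order, fit thresholds and slope codes (section 3.5); three waves (section 5.3); target N=1000 complete at all three (section 3.6). The plan gives no acceptance rate, covariance, slope variance or error variance, so it has no figure of its own to reproduce here.

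**Assumptions.** Intercept variance 14.4, slope variance 0.50 per 3-month unit, error variance 5.5 at every wave, mean 7 falling 0.3 per unit, loadings 0, 1, 3, normal complete data. Intercept-slope equality is read as equal variances. Observed-score intercepts are taken as 0 in the fitted model, the usual set-up; section 3.5 says so only for the scoring step.

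**Step 1: the sequence.** Three waves give 3 means + 3 variances + 3 covariances = 9 moments.

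| Model | Parameters | df |
|---|---|---|
| All constraints | 2 | 7 |
| Error variances freed | 4 | 5 |
| Means freed | 6 | 3 |
| Intercept and slope variances separate, covariance 0 | 7 | 2 |
| Covariance freed | 8 | 1 |

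The zero-mean steps have population RMSEA above 0.7. In simulation with similar variances, none of the first three models passed at N=1000.

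**Step 2: why slope variance moves.** With free error variances the three variances are reproduced whatever the slope, so only the between-wave covariances inform it. With covariance c, these are:
- waves 1 and 2: 14.4 + c
- waves 1 and 3: 14.4 + 3c
- waves 2 and 3: 14.4 + 4c + 3 × 0.50

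The zero-covariance model makes the first two equal and sets the third higher by 3 × slope variance. Averaging the first two gives a fitted slope variance of about 0.50 + (4c - 2c)/3 = 0.50 + 2c/3. Here c = correlation × √(14.4 × 0.50) = correlation × 2.683.
- Correlation -0.2: c = -0.537, giving 0.50 - 0.358 = 0.142 (maximum likelihood gives 0.158).
- Correlation -0.1: c = -0.268, giving 0.321, or 64% of 0.50.
- Correlation -0.3: c = -0.805, giving -0.037, so the estimate goes to 0.
- Correlation +0.3: 0.50 + 0.537 = 1.037, about double.

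**Step 3: how often the model passes.** RMSEA is below .05 when chi-square < df × (1 + 0.0025 × (N - 1)). For 2 df and N=1000 this is 2 × 3.4975 = 6.995. RMSEA is the criterion that bites: at -0.2 the population values are CFI 0.997 and RMSEA 0.047. The approximation below is a noncentral chi-square probability with noncentrality 999 × 2 × RMSEA².

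| Correlation | Population RMSEA | Accepted, approximation | Accepted, simulation | Slope variance (true 0.50) |
|---|---|---|---|---|
| -0.5 | 0.134 | 0% | 0% | not accepted |
| -0.3 | 0.071 | 24% | 12-23% | near 0 |
| -0.2 | 0.047 | 62% | 56-60% | about 0.15 |
| -0.1 | 0.024 | 90% | 89% | about two thirds kept |
| +0.3 | 0.071 | 24% | 25% | about doubled |

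**Step 4: sensitivity.** With three waves at loadings 0, 1, 4, acceptance is about 33% at -0.2 and 4% at -0.3. With intercept variance 12, error variance 5 and slope variance 1.0 / 0.5 / 0.25, acceptance at -0.2 is 30% / 59% / 77%, keeping 0.59 / 0.35 / 0.17 of the slope variance. Other variance mixes at -0.3 give acceptance from 0% to 66%.

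**Step 5: what freeing the errors first does.** In the same three settings at -0.3, the zero-covariance model keeps 0.34 / 0.05 / 0.00 of slope variance with free error variances and 0.71 / 0.58 / 0.40 with equal ones. Its pass rates are 5% / 20% / 41% and 1% / 20% / 51%. The order does not generally raise the pass rate; it enlarges the distortion once the model has passed.

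**Step 6: the alternative.** Two means, two variances, one covariance and one error variance make 6 parameters and 3 df. At N=1000 this model was accepted in 97-100% of samples, with slope variance 0.49-0.51.

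**The case against.** The strongest reply is that the effect is conditional. At a correlation of -0.5 the fit rule rejects the wrong model and the covariance is estimated, as intended. At -0.1 the model usually passes but most slope variance remains. Frequent acceptance and heavy loss coincide only around -0.2 to -0.3 with small slope variance. This stands, and the point is limited accordingly.

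Several stronger readings are tempting and not supported:
- **That predictors of slope could not be found.** With a predictor shifting slope by 0.15 per SD (assumed) and N=1000, accepted zero-covariance models at -0.2 detected it in 83% of samples, against 96% under the alternative. At -0.3 it was 56% against 98%, but there the wrong model is accepted in a minority of samples. This is lost power, not impossibility.
- **That free error variances are why the wrong model passes.** Step 5 shows otherwise.
- **That the RMSEA threshold must go.** A correct 1-df model fails it with probability P(chi-square > 3.4975) = 6% at N=1000. Keeping or dropping it is a matter of preference.
- **That the scoring step contradicts the selected model.** The text does not say which variances are held equal. If error variances are meant, the scores would not come from a model that has freed them; otherwise there may be no conflict.

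The four slope codes also matter. With four occasions at the listed codes, the zero-covariance model at -0.3 would keep 0.59 to 0.92 of slope variance. But only three waves are scheduled, and that mismatch is a separate matter. Finally, the alternative's good recovery assumes equal true error variances, which is why its likelihood-ratio check is needed.

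**Conclusion.** The point holds in conditional form. The order gives up equal error variances for HADS without a fair test and can retain a false zero covariance. The resulting slope variance may be too small, nearly right or too large, according to the sign and size of a covariance that the sponsor cannot know beforehand. The worst region under the assumed variances is a weak-to-moderate negative correlation, where about 70% of slope variance is lost at -0.2 ((0.50 - 0.15)/0.50).

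The consequence is biased slope variance and reduced power for predictors of slope, within a secondary or exploratory objective. A reader might infer that the main findings are at risk; they are not, because the primary prevalence estimate does not use the growth models. All sizes rest on the assumed variances, normal complete data, three waves and the reading of equality as equal variances. Severity: should be fixed.

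**What to change.** Rewrite the model-building sentences of section 3.5:
- Start with intercept and slope means, variances and their covariance all estimated and error variances equal (3 df with three waves).
- Free the error variances only if a likelihood-ratio test requires it.
- Do not use zero means, intercept-slope equality or zero covariance as starting constraints.
- Compute the individual scores from the selected model, and state which variances are held equal at that step.
- CFI and RMSEA can still be reported.

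The cost is one paragraph and no new data. Relative to a zero-covariance model, one more parameter is estimated, so slope estimates are slightly less precise if the true covariance is zero.

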
Where patients consent to taking part in the study using the online consent form, they will be asked to enter their name and email address, and whether they are happy to be contacted by email, post and/or phone. If patients decide not to provide an email address or their name, the study team will still be able to identify which patient has responded as the link to that consent form is unique to the patient and the REDCap record identifier can be cross referenced with the screening log. Where patients do not consent to taking part in the study, no personal information will be requested.

Eligible patients, who have not already opted out, will be invited to participate in an online questionnaire at 3, 6 and 12 months following discharge from ICU, or alternatively a paper copy of the questionnaire can be sent to them at the relevant time points or they may choose to answer the questionnaire over the phone with a member of the study team documenting their responses on REDCap. Prior to patient contact, electronic healthcare records will be accessed, and/or contact made with the patient's registered general practitioner, to confirm the patient's survival status. This is intended as a pre-contact check to minimise distress caused to families/relatives by making contact in the event a patient has died following discharge from the ICU.

For patients who have provided their email address, an email will be sent at 3, 6 and 12 months with a unique link to their survey. The link to their survey at each timepoint will expire after 1 month. At the beginning of the questionnaire, the study information will be repeated. Patients will be able to leave the study by contacting their local study team at any point during the study. If patients indicate they would prefer to complete a paper version, they will be provided with a pre-paid envelope to return their completed questionnaire. If patients indicate they would like to complete their questionnaire over the phone, this can be arranged with a study team member.

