#### **Psychological assessment via self-reported questionnaire:**

The following four self-report questionnaires will be administered at 3, 6 and 12 months following ICU discharge:

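### Section 3.5 gives four slope loadings per growth model for outcomes measured three times, and its quadratic set does not represent curvature

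*Combined protocol and SAP*

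**What the plan says.** Section 3.5 plans latent growth models for anxiety, depression and trauma scores. It describes the two growth factors as "the intercept (value of the initial observation) and slope (the rate of change from this observation over time", and sets the time scores as "linear models being defined as slope parameters 0, 1, 4, and 12 and quadratic slopes as 0, 1, 8 and 24". Constraints are relaxed in a listed order until CFI exceeds .95 and RMSEA is below .05. Individual intercept and slope scores are then predicted and related to the predictor variables.

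The data collection sections give three occasions throughout:
- Section 3.6: recruitment may stop "when 1000 patients have answered the questionnaire at all three time points".
- Section 4.1: patients are told of "the possibility of receiving three questionnaires during the year following discharge".
- Section 5.2: patients "will be invited to participate in an online questionnaire at 3, 6 and 12 months following discharge from ICU".
- Section 5.3: "The following four self-report questionnaires will be administered at 3, 6 and 12 months following ICU discharge". The word four here counts instruments, not occasions.

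Section 5.3 lists no HADS or IES-6 at ICU discharge.

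**The concern.** A loading is the time score attached to one observed occasion, so three occasions take three loadings. With four listed, the analyst must drop one or substitute the visit times, and nothing in the plan guides that choice. The intercept is defined at the first observation, which is the 3-month questionnaire, so the scores should count from there.

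The quadratic set raises a separate problem. A quadratic term needs the squares of the time scores, and these values are not squares. The plan also does not say whether the quadratic slope replaces the linear slope or is added to it as a third factor.

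At stake is the objective on "predictors of depression, anxiety and/or trauma symptoms at 3-, 6- and 12-months after ICU discharge", because the predictor analysis uses the individual intercept and slope scores from these models. Section 3.2 lists that objective as exploratory; the Study Summary (Section 1) lists it as secondary. If loadings are chosen after fit has been inspected, this analysis is no longer pre-specified.

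**Working it through.** **1. Scores implied by the schedule.** Visits at 3, 6 and 12 months with the origin at the first give 3−3, 6−3, 12−3 = 0, 3, 9 months, or 0, 1, 3 in 3-month units. The squares are 0, 9, 81, or 0, 1, 9.

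**2. Could a discharge wave explain four loadings?** Months 0, 3, 6, 12 divided by 3 give 0, 1, 2, 4. The plan has 0, 1, 4, 12.

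**3. Which three of the four linear values match?** The schedule's interval ratio is (12−6)/(6−3) = 2.

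| Subset | Interval ratio |
|---|---|
| 0, 1, 4 | 3/1 = 3 |
| 0, 1, 12 | 11/1 = 11 |
| 0, 4, 12 | 8/4 = 2 |
| 1, 4, 12 | 8/3 = 2.67 |

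Only 0, 4, 12 matches. Its unit is 9 months/12 = 0.75 month.

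**4. The quadratic set.** The squares of 0, 1, 4, 12 are 0, 1, 16, 144, not 0, 1, 8, 24. The stated set is twice the linear set except at the second value (1 instead of 2). In the matching subset, 0, 8, 24 = 2 × (0, 4, 12), so it is the same model with the slope rescaled.

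**5. Size, for a truly linear course (assumed values).** The plan gives no variances, so I assumed a slope of −0.5 HADS points per 3 months (9-month change 3 × −0.5 = −1.50), intercept variance 14, slope variance 0.5 (over the span 0.5 × 3² = 4.50), intercept-slope covariance 0 and error variance 6.

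The true variance at time t is 14 + 0.5t² + 6, giving 20, 20.5, 24.5 at t = 0, 1, 3. The covariance between times s and t is 14 + 0.5st, giving 14, 14, 15.5.

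The fitted model has 2 means, 2 variances, 1 covariance and 1 common error variance: 6 parameters. Three waves supply 3 means + 6 variances and covariances = 9 moments, so df = 3. RMSEA = √(F/df), where F is the minimised maximum likelihood discrepancy for means and covariances.

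| Loadings | 9-month change | RMSEA |
|---|---|---|
| 0, 4, 12 | −1.50 | 0.000 |
| 1, 4, 12 | −1.47 | 0.021 |
| 0, 1, 4 | −1.46 | 0.029 |
| 0, 1, 12 | −1.33 | 0.081 |
| 0, 8, 24 | −1.50 | 0.000 |
| 1, 8, 24 | −1.49 | 0.010 |

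- With 0, 1, 12 the change is 1 − 1.33/1.50 = 11% too small. Slope variance over the span is 3.17, which is 1 − 3.17/4.50 = 30% low.
- With 0, 1, 4 slope variance is 4.22, or 6% low.
- With 1, 4, 12 the intercept is no longer the first observation.
- On this straight line the quadratic 1, 8, 24 fits better than the linear 1, 4, 12.

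**6. Sensitivity for 0, 1, 12.** RMSEA is 0.073 with the covariance fixed at zero, 0.107 with slope variance 1, 0.136 with slope −1, and 0.152 with both changes.

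**7. A curved course (assumed means 8, 6.5, 6.5).** Loadings 0, 4, 12 and 0, 8, 24 both give RMSEA 0.184 and CFI 0.927: the same misfit twice. A mean-only quadratic term on 0, 1, 9 beside a linear slope on 0, 1, 3 fits these means exactly: 8 − 2t + 0.5t² gives 8, 6.5 and 8 − 6 + 4.5 = 6.5.

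**8. Identification of a quadratic factor with three waves and equal error variances.** There are 9 moments. Parameter counts are 7 with all factor covariances zero (3 means, 3 variances, 1 error; df 2), 8 with only the intercept-slope covariance free (df 1), and 10 with all three covariances free. The last is not identified.

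**The case against.** The strongest reply is that the harm is limited. A linear model on three waves can be estimated once three scores are chosen. The subset with the right spacing recovers the true change exactly, and a change of time unit does not alter the sign or test of any predictor of slope. The mismatch would also surface as soon as the model was set up. The worst linear choice, 0, 1, 12, is the least plausible one, and it misses by 1.50 − 1.33 = 0.17 points on a 0–21 subscale. All of this stands. The effect on the predictor regressions themselves has not been quantified.

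A second reply is that the comparison of linear with quadratic is empty only when the 1 is dropped. That is correct: on the curved means, 0, 1, 4 gives RMSEA 0.202 and 0, 1, 8 gives 0.225. Those fits differ, but both are poor, and neither set is correctly spaced or squared.

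A third concerns 0, 1, 4 with slope −1 and slope variance 1. Its RMSEA is 0.056 with the covariance free but 0.049, a pass, with the covariance at zero and equal error variances. However, Section 3.5 relaxes the equal-error constraint first, and with that relaxed and the covariance still zero the value is again 0.056. This case is borderline and the conclusion does not depend on it.

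The flowchart in Appendix 2 could not be read here, but the written schedule is uniform across four sections.

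**Conclusion.** The concern holds. The contradiction between four loadings and three measurement occasions, and the failure of the quadratic set to be a squared-time set, follow from the plan's own figures and need no assumption. No reading of the stated values gives both the right spacing and a test of curvature.

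The practical size does rest on assumed variances and slopes. It runs from a harmless change of unit (0, 4, 12) to an 11% understatement of change, a 30% understatement of slope variance and a failed RMSEA rule for a course that is truly linear (0, 1, 12). Under the base assumptions only 0, 1, 12 fails among the linear subsets.

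This should be corrected before analysis, because the intercept and slope scores feed the predictor work. It does not touch the primary 6-month proportion in Section 3.2.

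**What to change.** In Section 3.5:
- Replace the linear loadings with 0, 3, 9 (months since the first questionnaire), or equivalently 0, 1, 3 in 3-month units, and state the unit.
- Delete 0, 1, 8, 24. Define the quadratic loadings as 0, 9, 81 (or 0, 1, 9 in 3-month units).
- State whether the quadratic term is added to the linear slope. A mean-only term added to it is one workable form: 7 parameters against 6 for the linear model with equal error variances, so curvature is tested on one degree of freedom.
- If a random quadratic factor is wanted, state its covariance constraints, since leaving all factor covariances free is not identified.

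The cost is wording in one section, handled through the amendment route in Section 7.7 if the sponsor judges that it applies. No additional patients, visits or data are required.
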